3.2 Primary outcome variable

The proportion of participants with an Investigator Global Assessment (IGA) 0/1 and a decrease in IGA of ≥ 2 points at Week 16 relative to baseline will be used as the primary efficacy variable.

The IGA is an instrument used in clinical studies to rate the severity of AD globally, based on a 5-point scale ranging from 0 (clear) to 4 (severe). The IGA uses clinical characteristics of erythema, infiltration, papulation, oozing, and crusting as guidelines for the overall severity assessment. The validated IGA scale for AD will be completed by the Investigator on an electronic device supplied to the site according to the Schedule of Activities (SoA) (CSP Table 3) to capture these key measures of AD disease activity and describe the overall appearance of AD lesions (Table 4).

Table 4 Investigator Global Assessment Score

Score	Morphological description
0 – Clear	No inflammatory signs of atopic dermatitis (no erythema, no induration/papulation, no lichenification, no oozing/crusting). Post-inflammatory hyperpigmentation and/or hypopigmentation may be present.
1 -- Almost clear	Barely perceptible erythema, barely perceptible induration/papulation, and/or minimal lichenification. No oozing or crusting.
2 -- Mild	Slight but definite erythema (pink), slight but definite induration/papulation, and/or slight but definite lichenification. No oozing or crusting.
3 -- Moderate	Clearly perceptible erythema (dull red), clearly perceptible induration/papulation, and/or clearly perceptible lichenification. Oozing and crusting may be present.

Table 4 Investigator Global Assessment Score

Score	Morphological description
4 -- Severe	Marked erythema (deep or bright red), marked induration/papulation, and/or marked lichenification. Disease is widespread in extent. Oozing or crusting may be present.

A responder at Week 16 is defined as having IGA 0/1 and a decrease in IGA of ≥ 2 points at Week 16 relative to baseline.

In the statistical analyses, a binary variable will take on value 1 if a participant is defined as a responder, and value 0 for non-responder, and will be used as the response variable for the efficacy analysis.

Intercurrent events will be considered as described above in Section Intercurrent Events (Section 3.1.5). Intercurrent events will be considered for analyses and descriptive summaries.

3.3 Secondary outcome variables

3.3.1 Eczema Area and Severity Index (EASI)

The first and third key secondary efficacy variables, derived from Eczema Area and Severity Index (EASI), are the proportion of participants with skin clearance EASI-75 and EASI-90, respectively, at Week 16.

The EASI is a continuous outcome that will be assessed by the Investigator or designee at the visits specified in the SoA (CSP Table 3) on an electronic device supplied to the site. The EASI is a validated tool used in clinical practice and clinical trials to assess the severity and extent of AD (Hanifin et al 2001).

Severity of 4 AD disease characteristics (erythema, induration/papulation, excoriation (scratching), and lichenification) will each be assessed on a scale of 0 (absent) to 3 (severe) in each of 4 body regions (head/neck, trunk, upper limbs, and lower limbs). In addition, the area of AD involvement will be assessed as a percentage by body area in the 4 anatomic areas (head/neck, trunk, upper limbs, and lower limbs) and scored as 0 (no eruption), 1 (1% to 9%), 2 (10% to 29%), 3 (30% to 49%), 4 (50% to 69%), 5 (70% to 89%), or 6 (90% to 100%). The total score for each region is the severity score multiplied by the area score and a multiplier. The multipliers are as follows: head/neck=0.1, trunk=0.3, upper extremities=0.2, lower extremities=0.4. The total body total score is the sum of the region total scores. For each body region the severity scores and area of involvement scores are combined by the ePRO device into a domain score for each body region. The total EASI score will be calculated by the ePRO device by adding the four body region domain scores and ranges from 0 to 72. The ePRO does not allow for questions to be unanswered, so no consideration is required for missing items.

The percentage of participants achieving a 50% reduction from baseline in EASI total score (EASI-50), 75% reduction from baseline in EASI total score (EASI-75), 90% reduction from baseline in EASI total score (EASI-90), and 100% reduction from baseline in EASI total score (EASI-100) will be calculated from the total EASI scores.

The first and third key secondary endpoints are binary responses that classify a participant's skin clearance at Week 16 using the EASI:

- EASI-75 response rate: Participants will be classified as responders if they achieve at least a 75% reduction from baseline in their EASI total score at Week 16. Otherwise, participants will be classified as non-responders.
- EASI-90 response rate: Participants will be classified as responders if they achieve at least a 90% reduction from baseline in their EASI total score at Week 16. Otherwise, participants will be classified as non-responders.

In the statistical analyses, a binary variable will take on value 1 if a participant is defined as a responder, and value 0 for non-responder, and will be used as the response variable for the efficacy analysis.

Intercurrent events for responder analyses will be considered as described above in Section Intercurrent Events (Section 3.1.5). Participants with a missing baseline EASI total score will have missing change from baseline status and thus missing responder status at post baseline visits. Intercurrent events will be considered for analyses and descriptive summaries.

The proportion of participants with skin clearance EASI-50 and EASI-100, respectively, at Week 16 are secondary endpoints and derived as described for the key secondary endpoints above.

Changes from baseline in EASI total score at Week 16 will be analyzed as a secondary endpoint.

Changes from baseline in EASI total score at Week 52 will be analyzed. The proportion of participants with skin clearance EASI-75 at Week 52 will be analyzed.

For change from baseline analyses, intercurrent events will be considered as described above in Section Intercurrent Events (Section 3.1.5). Intercurrent events will be considered for analyses and descriptive summaries.

3.3.2 Peak Pruritus Numeric Rating Scale

The proportion of participants with an improvement of ≥ 4 points in peak pruritus weekly score at Week 16 will be used as the second key secondary efficacy variable.

The Peak Pruritus NRS is a one-item daily assessment of the worst itch the participant experienced over the past 24 hours. This is recorded every evening from Visit 1 onwards on the electronic device supplied to the participants. The score ranges from 0 to 10, with 0 being “no itch” and 10 being “worst itch imaginable.” and so a reduction in score is considered an improvement.

If a participant has at least 4 non-missing daily scores in a 7-day week, the peak pruritus weekly score is defined as the sum of the available daily scores divided by the number of days with non-missing daily scores. If there are less than 4 non-missing daily scores, then the weekly score is missing for that week.

The second key secondary endpoint is a binary response that will classify a participant as a responder if there is an improvement of 4 or more points in peak pruritus weekly score at Week 16 relative to baseline. Otherwise, participants will be classified as a non-responder.

In the statistical analyses, a binary variable will take on value 1 if a participant is defined as a responder, and value 0 for non-responder, and will be used as the response variable for the efficacy analysis.

The change from baseline in peak pruritus score at Week 2 will be analyzed as a secondary endpoint.

Intercurrent events will be considered as described above in Section Intercurrent Events (Section 3.1.5). Participants with a missing baseline score will have missing change from baseline status. Intercurrent events will be considered for analyses and descriptive summaries.

3.3.3 Patient-Oriented Eczema Measure (POEM)

The change from baseline in Patient-Oriented Eczema Measure (POEM) score at Week 16 will be analyzed as a secondary endpoint.

The POEM is a continuous outcome that will be completed at the on-site visits specified in the SoA (CSP Table 3) on an electronic device supplied to the site.

The POEM is a 7-item assessment of AD symptoms (itchiness, sleep disturbance, bleeding, weeping, cracking, flaking, and dryness) that characterizes severity as a function of symptom frequency. The participant responds to each of the 7 questions by selecting the approximate number of days “over the last week” when they experienced the symptom, scored as 0 (no days), 1 (1 to 2 days), 2 (3 to 4 days), 3 (5 to 6 days), or 4 (every day).

The seven items are summed, resulting in a score ranging from 0 to 28 (Table 5). Higher scores represent more severe AD symptoms.

Table 5 Patient-Oriented Eczema Measure Score Bands

Score range	Clinical interpretation
0 to 2	Clear or almost clear
3 to 7	Mild atopic dermatitis
8 to 16	Moderate atopic dermatitis
17 to 24	Severe atopic dermatitis
25 to 28	Very severe atopic dermatitis

The ePRO does not allow for questions to be unanswered, so no consideration is required for missing items.

Intercurrent events will be considered as described above in Section Intercurrent Events (Section 3.1.5). Intercurrent events will be considered for analyses and descriptive summaries.

Changes from baseline in POEM score at Week 52 will be analyzed.

3.3.4 Scoring Atopic Dermatitis (SCORAD)

The change from baseline in SCORing Atopic Dermatitis (SCORAD) score at Week 16 will be analyzed as a secondary endpoint.

SCORAD is a continuous outcome that will be completed at the on-site visits specified in the SoA (CSP Table 3) on the electronic device supplied to the site.

SCORAD is a clinical tool for assessing the severity of AD that evaluates the extent and intensity of AD lesions, in addition to subjective symptoms (Kunz et al 1997). There are 3 components to the assessment: A = extent or affected body surface area, B = severity, and C = subjective symptoms. For component A; the extent of AD is assessed as a percentage of each defined body area (head/neck, anterior trunk, back, upper limbs, lower limbs and genitals) (see CSP Section 8.1.4) and is reported as the sum of all areas, with a maximum score of 100%. For component B, the severity of 6 specific symptoms of AD (redness, swelling, oozing/crusting, excoriation, skin thickening/lichenification, dryness) is assessed using the following scale: 0 (none), 1 (mild), 2 (moderate), or 3 (severe), giving a maximum of 18 total points. For component C, subjective assessments of itch and sleeplessness are recorded for each symptom by the participant or relative on a visual analogue scale (VAS), where 0 is no itch or sleeplessness and 10 is the worst imaginable itch or sleeplessness) respectively. The VAS scores are summed to give a maximum possible score of 20. The SCORAD total score is calculated by the ePRO device using an algorithm $(A/5+7(B/2)+C)$. The maximum total score is 103, with higher values indicating more severe disease. The ePRO does not allow for questions to be unanswered, so no consideration is required for missing items.

Intercurrent events will be considered as described above in Section Intercurrent Events (Section 3.1.5). Intercurrent events will be considered for analyses and descriptive summaries.

Changes from baseline in SCORAD total score at Week 52 will be analyzed.

3.3.5 Dermatology Life Quality Index (DLQI)

The change from baseline in Dermatology Life Quality Index (DLQI) total score at Week 16 will be analyzed as a secondary endpoint.

The DLQI is a continuous outcome that will be completed at the on-site visits specified in the SoA (CSP Table 3) on the electronic device supplied to the site. The DLQI will only be completed by participants who are age 17 or older at Visit 1.

The DLQI is a 10-item assessment of dermatology-specific health-related quality of life in participants age 17 and older (Finlay and Khan 1994). Participants are asked to rate their symptoms and the impact of their symptoms “over the last week” on several domains: symptoms and feelings, daily activities, leisure, work and school, personal relationships, and treatment. Both the total score and domain scores will be calculated.

Each item (except question 7) is rated on a four-point Likert scale: 3 = very much, 2 = a lot, 1 = a little, 0 = not at all, 0 = not relevant, and 0 = question unanswered. Scoring question 7, the first part asks: 'Over the last week, has your skin prevented you from working or studying?' Scoring is for response of Not relevant = 0, and Yes = 3 (as 'prevention' is the biggest possible impact it is scored the maximum of 3). If response is No, a further question is asked: 'How much has your skin been a problem at work or studying', and scored as: A lot = 2, A little = 1, Not at all = 0.

The subscale domain scores are the sum of the individual question scores. If one question is left unanswered, the corresponding subscale should not be scored. The six domain scores are as follows:

Table 6 Dermatology Life Quality Index Domain Scores

Score range	Domains
0 to 6	Symptoms and feelings: Questions 1 (itchy, sore, painful or stinging) and 2 (embarrassed, self-conscious)
0 to 6	Daily activities: Questions 3 (interfered shopping or at home) and 4 (influenced the clothes)
0 to 6	Leisure: Questions 5 (affected social/leisure activities) and 6 (difficult to do any sport)
0 to 3	Work and school: Question 7 (prevented working or studying)
0 to 6	Personal relationships: Questions 8 (problems with partner, friends, relatives) and 9 (caused sexual difficulties)
0 to 3	Treatment: Question 10 (problem using treatment)

The domain subscales for each domain will be presented as a percentage of the maximum score (either 6 or 3).

The DLQI total score is calculated by summing the score of each question, resulting in a maximum of 30 and a minimum of 0. If one question is unanswered, this is allocated a score of 0 and the DLQI score summed in the usual way, out of 30. If two or more questions are unanswered, the questionnaire is not scored. The higher the score, the more quality of life is impaired.

The effects of life scores are calculated as follows from the total score:

- 0-1 = no effect at all on participant's life,
- 2-5 = small effect on participant's life,
- 6-10 = moderate effect on participant's life,
- 11-20 = very large effect on participant's life,
- 21-30 = extremely large effect on participant's life.

Intercurrent events will be considered as described above in Section Intercurrent Events (Section 3.1.5). Intercurrent events will be considered for analyses and descriptive summaries.

Changes from baseline DLQI total score at Week 52 will be analyzed.

3.3.6 Children's Dermatology Life Quality Index (CDLQI)

The change from baseline in Children's Dermatology Life Quality Index (CDLQI) total score at Week 16 will be analyzed as secondary endpoint.

The CDLQI is a continuous outcome that will be completed at the visits specified in the SoA (CSP Table 3) on the electronic device supplied to the site. The CDLQI will only be completed by participants who are age 16 or younger at Visit 1 in regions where adolescent recruitment is permitted.

The CDLQI is a 10-item assessment of dermatology-specific health-related quality of life in children and adolescents ages 5 to 16 (Lewis-Jones and Finlay 1995). Participants are asked to rate their symptoms and the impact of their symptoms "over the last week" on several domains: symptoms and feelings, leisure, school and holidays, personal relationships, sleep, and treatment.

Each item is rated on a four-point Likert scale: 3 = very much, 2 = quite a lot, 1 = only a little. 0 = not at all, 0 = question unanswered, and for Question 7 additionally 3 = prevented school. Both the total score and domain scores will be calculated.

The subscale domain scores are the sum of the individual question scores. If one question is left unanswered, the corresponding subscale should not be scored. The six domain scores are calculated as follows:

Table 7 Children’s Dermatology Life Quality Index Domain Scores

Score range	Domains
0 to 6	Symptoms and feelings: Questions 1 (scratchy, sore, painful) and 2 (embarrassed, self-conscious, upset, sad)
0 to 9	Leisure: Questions 4 (worn different or special clothes/shoes), 5 (affected going out, playing, doing hobbies) and 6 (avoided swimming or other sports)
0 to 3	School or holidays: Question 7 (affected school work/holiday)
0 to 6	Personal relationships: Questions 3 (affected your friendships) and 8 (calling you names, teasing, bullying, asking questions or avoiding you)
0 to 3	Sleep: Question 9 (sleep been affected)
0 to 3	Treatment: Question 10 (problem with treatment)

The CDLQI total score ranges from 0-30. The total score is the sum of the individual question scores. If one question is left unanswered, this is scored 0 and the scores are summed and expressed as usual out of a maximum of 30. If two or more questions are left unanswered, the questionnaire is not scored.

Meaning of total score:

- 0-1 = no effect on child’s life,
- 2-6 = small effect child’s life,
- 7-12 = moderate effect child’s life,
- 13-18 = very large effect child’s life,
- 19-30 = extremely large effect child’s life.

Intercurrent events will be considered as described above in Section Intercurrent Events (Section 3.1.5). Intercurrent events will be considered for analyses and descriptive summaries.

Changes from baseline CDLQI total score at Week 52 will be analyzed.

3.3.7 Serum benralizumab concentration

All PK samples will be collected before administration of study medication in accordance with the visit schedule provided in Table 3 of the CSP. For the PK analysis, it is important that the date, time, and location of each subcutaneous (SC) injection is recorded for each participant.

Concentration results below the lower limit of quantification will be set to lower limit of quantification (LLOQ)/2 for analysis and will be listed as <LLOQ.

Drug concentration information that would unblind the study will not be reported to investigative sites or blinded personnel until the study has been unblinded.

All available data will be included, regardless of intercurrent events like taking rescue medication or withdrawal from study.

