[Figure 1](#) presents an overview of investigational product (IP) administration for each randomized treatment group.

Figure 1 Investigational Product Administration Q4W by Randomized Treatment Sequence

^a In the extension phase, participants will receive benralizumab on a Q8W or Q4W dosing regimen, as predetermined at randomization (Visit 2). Participants randomized to receive benralizumab Q8W in the extension phase will also receive placebo at intervening study visits when they are not receiving benralizumab.

Q4W, every 4 weeks; Q8W, every 8 weeks.

All participants who prematurely discontinue IP (IPD) should return to the study site for the IPD visit 4 weeks (± 7 days) after the last dose of IP for procedures, or as soon as feasible if this interval is missed (eg, if decision on discontinuation was made later), as specified in Table 3 of the CSP.

[figure not shown]
At the IPD visit, the participant will be offered the following options for further follow-up:

- Participants are encouraged to return to all scheduled site visits and perform all procedures but without IP administration, until the end of the study (Visit 16).
- Participants unwilling or unable to attend the scheduled site visits until the end of the double-blind treatment period, will be offered a follow-up option that includes monthly telephone contact instead. During follow-up telephone contact, the Investigator will collect information about concomitant medications, information on AD symptoms, and AE/SAE(s).

All Week 16 analyses at primary database lock (DBL) will evaluate the two initial dose treatment arms: benralizumab 30 mg (total $n = 80$), and placebo (total $n = 80$). Analyses of data for Week 52 end of study reporting will include data from the entire study, presenting the three randomized treatment groups: benralizumab followed by Q4W, benralizumab followed by Q8W and placebo followed by benralizumab Q4W-Q8W.

For an overview of the study design, see [Figure 2](#). For further details see CSP Section 4.1.

Figure 2 Study Design

^a To maintain blinding, participants will receive investigational product every Q4W during the extension period. Placebo will be administered Q8W, occurring 4 weeks after each benralizumab administration. n, number; Q4W, every 4 weeks; Q8W, every 8 weeks.

Participants and Investigators will remain blinded to the treatment and regimen until the final DBL.

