3.1.5 Intercurrent Events

Intercurrent events are withdrawal from the study at any time or requiring rescue therapy from Day 29 onwards. However, participants who started on placebo and switched to benralizumab in the extension phase are additionally permitted rescue therapy for 28 days from starting benralizumab, and thus additionally any rescue therapy use from Day 141 (ie 29 days after first dose of benralizumab) onwards will be considered as intercurrent event for these participants.

Withdrawal from the study will be considered from the day after withdrawal onwards, thus data on the day of withdrawal will be used as recorded. Rescue therapy from Day 29 (of first dose, and additionally for placebo-benralizumab participants from first benralizumab dose) onwards will be considered for intercurrent event imputation from the day of taking rescue medication onwards.

For responder or binary analyses, participants with intercurrent events will be considered as non-responders from the time these events occur. Participants with missing data for binary endpoints will also be considered non-responders at affected post baseline visits. Intercurrent events will be considered for analyses and descriptive summaries.

For change from baseline analyses or number and percentage of score category summaries, participants with intercurrent events will be considered as having missing scores from the time these events occur. Intercurrent events will be considered for analyses and descriptive summaries.

For summaries of number and percentage of individual questionnaire scores, all data will be presented as recorded, without imputation for intercurrent events.

The categorisation and imputations of responder status and reasons for non-response are provided in following table.

Table 3 Response Category Imputations

Response Category	Imputation Rule
Responder	Keep data as recorded, unless after taking rescue medication
Non responder	
Recorded as non-responder	Keep data as recorded, even if after taking rescue medication

Table 3 Response Category Imputations

Response Category	Imputation Rule
Missing	For missing questionnaire/visit, where participant remains in study and could be Responder or Recorded Non-responder or Rescue medication and remain in study
Rescue medication and remain in study	Impute if recorded as Responder and participant ongoing in study. Impute from day of rescue medication onwards, but only for assessments where participant is a Recorded Responder

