4 ANALYSIS METHODS

The primary DBL is targeted to occur when all participants have completed the 16-week placebo-controlled treatment period. The final DBL will occur when all participants have completed the 52-week treatment period and the Week 60 follow-up visit and/or the IP discontinuation (IPD) /EOT visit.

All data will be included in the analyses, regardless of whether IP was prematurely discontinued or delayed, and irrespective of protocol adherence, unless the participant withdrew consent to further study participation.

All personnel involved in the analyses of the study will remain blinded until the primary DBL and protocol deviations are identified.

The CSR will be based on the final DBL.

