4.2.7.9 Serum benralizumab concentration

Serum benralizumab concentration will be summarized using descriptive statistics at each visit by treatment group based on the PK analysis set.

Serum benralizumab concentrations will be presented for both, the 16-week placebo-controlled treatment period and the Week 52 end of study reporting.

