8.2.4 ADA and PK

Benralizumab serum concentrations will be summarized by visit and ADA status (treatment emergent ADA positive, ADA negative, ADA persistently positive, ADA positive with titre > median of maximum titre) for participants in the PK analysis set, if enough data are available.

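### The by-visit concentration and ADA–PK summaries pool on-dosing samples with samples taken after IP was stopped, so group means understate on-treatment exposure

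*SAP*

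**What the plan says.** Estimating the PK of benralizumab 30 mg is a secondary objective (SAP Table 1). The planned output is in Section 4.2.7.9: "Serum benralizumab concentration will be summarized using descriptive statistics at each visit by treatment group based on the PK analysis set". Appendix 8.2.4 adds: "Benralizumab serum concentrations will be summarized by visit and ADA status", for the PK analysis set and only if there are enough data.

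Three statements decide which samples enter:

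- Section 3.3.7: "All available data will be included, regardless of intercurrent events like taking rescue medication or withdrawal from study". The same section sets values below the quantification limit to LLOQ/2 for analysis.
- Section 4: "All data will be included in the analyses, regardless of whether IP was prematurely discontinued or delayed, and irrespective of protocol adherence". The only exception is withdrawal of consent.
- Section 1.1.1, for those who stop IP: "Participants are encouraged to return to all scheduled site visits and perform all procedures but without IP administration, until the end of the study". Those unwilling or unable to attend "will be offered a follow-up option that includes monthly telephone contact instead".

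The PK analysis set (Section 2.2.4) is defined by participant. It requires at least one quantifiable post-dose value and samples assumed to be unaffected by factors such as protocol deviations. Its list of excluding deviations is still to be fixed before database lock.

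**The concern.** A rule that keeps data after treatment has stopped suits a treatment-policy analysis of efficacy. It does not suit a description of the concentration that a regimen produces. Someone who stopped injections months earlier and still attends gives a low or unquantifiable sample, and that sample is averaged into the arm's figure for the visit as if dosing had continued.

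Two readings are at stake. The by-visit mean for an arm will be taken as exposure on that arm's regimen, in a study that also aims to identify a maintenance frequency. In the ADA–PK summary, a low concentration is low because dosing stopped, whatever the antibody status, so the table cannot separate an antibody effect from stopped dosing.

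The SAP draws such lines elsewhere. Adverse events have on-treatment windows tied to the last dose (Section 3.4.1), and ADA has a sample-level exclusion for samples taken after dosing on an administration day (Appendix 8.2). PK, which depends most directly on dosing, has neither.

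**Working it through.** **Do off-drug samples exist?** Yes, for those who take the first follow-up option in Section 1.1.1. The telephone option yields none. Section 4.2.1 counts participants who stopped IP but completed follow-up, so the SAP expects such a group.

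**Are they kept?** Section 4 keeps them explicitly. Section 3.3.7 points the same way but is the weaker text: its two examples are rescue and study withdrawal, and Section 3.1.5 says "Intercurrent events are withdrawal from the study at any time or requiring rescue therapy from Day 29 onwards", which leaves out IP discontinuation. Table 11, however, handles treatment discontinuation under its intercurrent-event strategies, and Appendix 8.1 counts early discontinuation among intercurrent events.

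**Does a filter remove them?** Not clearly. Section 2.2.4 works on whole participants and is framed around deviations. Stopping IP and staying in follow-up is provided for in the design. Excluding such a participant would also discard the valid on-dosing samples.

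**Size for one group.** The SAP gives no discontinuation rate, half-life or expected concentration, so there is no figure of its own to reproduce. Both inputs below are assumptions:

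- f = share of sampled participants who are off IP
- r = their concentration relative to the on-dosing mean

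Arithmetic mean ÷ on-dosing mean = 1 − f(1 − r).

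| f | r = 0 | r = 0.1 | r = 0.25 | r = 0.5 |
|---|---|---|---|---|
| 5% | 0.950 | 0.955 | 0.963 | 0.975 |
| 10% | 0.900 | 0.910 | 0.925 | 0.950 |
| 20% | 0.800 | 0.820 | 0.850 | 0.900 |

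With 40 planned per benralizumab sequence and all sampled, f = 10% is 4 participants. The median, also a listed statistic (Section 4.1), moves to the (0.5 − f)/(1 − f) quantile of the on-dosing values if every off-drug value lies below it. That is 0.4/0.9 = 0.444 at f = 10% and 0.3/0.8 = 0.375 at f = 20%.

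**Side-by-side readings.** At r = 0.1, the Q4W/Q8W ratio of means is multiplied by (1 − 0.9·f_Q4W)/(1 − 0.9·f_Q8W):

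- 10% and 10%: 0.910/0.910 = 1.00
- 5% and 15%: 0.955/0.865 = 1.10
- 15% and 5%: 0.865/0.955 = 0.91

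The absolute difference is multiplied by [(1 − 0.9·f_Q4W) − k(1 − 0.9·f_Q8W)]/(1 − k), where k is the true Q8W level relative to Q4W, assumed to be 0.3 to 0.5:

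- 10% and 10%: 0.91
- 5% and 15%: 0.99 to 1.05
- 15% and 5%: 0.83 to 0.78

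The ratio formula applies equally to ADA status. If 3 of 10 ADA-positive participants and 10% of ADA-negative participants were off drug, the positive/negative ratio would be multiplied by 0.73/0.91 = 0.80 with no antibody effect at all. With the shares reversed it would be 0.91/0.73 = 1.25.

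**The case against.** The strongest reply is that little depends on this. The PK outputs are descriptive, no test uses them, and Section 4.1 confines the statistical comparison of Q4W with Q8W to efficacy. Section 4.2.1 reports by visit how many participants have stopped IP but remain in follow-up, so a reader can see that dilution is possible. Appendix 8.2 lists concentration, titre and eosinophils for each ADA-positive participant. The exclusion list in Section 2.2.4 is open and could remove some of those who stopped.

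These points limit the consequence but do not remove the defect. A disposition count does not let a reader recover the on-dosing mean, and a participant-level list is the wrong tool for a sample-level problem.

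A reader might go further and infer that reported steady-state troughs and the Q4W/Q8W and ADA contrasts are all biased downwards. The SAP does not support that. It plans no steady-state parameter and no formal PK comparison of regimens. Only a single group's mean must fall; the contrasts can stay the same, shrink or grow. Nor should the loss be sized on a geometric mean, where it would look much larger, because neither Section 4.1 nor Section 4.2.7.9 lists one.

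**Conclusion.** The point stands as a correction to a secondary, descriptive output. As written, the SAP sends post-discontinuation samples into the by-visit and ADA-status concentration summaries, and nothing in Section 2.2.4 clearly takes them out.

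Any group with off-drug attenders will show a mean below its on-treatment exposure. For an assumed 5% to 20% off drug with residual levels of 0 to 0.5, the mean is 0.80 to 0.975 of the on-dosing value, and about 0.90 for 10% off drug near zero. The direction of any distortion between regimens or ADA groups depends on differential discontinuation, which the SAP does not give. The actual size is unknown until discontinuation and attendance are known. The primary, key secondary and other efficacy tests are unaffected.

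**What to change.** In Sections 3.3.7, 4.2.7.9 and 8.2.4, add a sample-level rule:

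- Flag each post-first-dose PK sample by time since the last active dose, using the injection dates that Section 3.3.7 already requires.
- Base the main by-visit and ADA-status summaries on samples from participants still on scheduled dosing.
- Show post-discontinuation samples in a separate summary by time since last active dose, or in listings.
- Keep at their own visits: pre-first-dose samples, placebo-arm samples before the Week 16 switch, samples at permitted postponed doses (Section 3.1.3), and any planned follow-up samples after the final Week 48 dose.

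The last item matters. A plain cut-off at the assigned dosing interval would drop follow-up samples even from fully compliant participants and would leave no place for samples taken before any active dose.

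The cost is a short paragraph, one derived flag and slightly fewer samples in the late-visit summaries. No data are discarded.
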